9.2 CAUSALITY

Relationship of the AE to the study drug should be defined as follows:

- None
- Unlikely
- Possible
- Probable

9.3 ADVERSE EVENTS REPORTING PROCEDURES

The following AEs will be reported and monitored for this study:

- Peripheral Neuropathy (all grades)
- All Grade 3 and 4 AEs
- Any AEs resulting in a missed dose, dose reduction, or treatment discontinuation
- All SAEs

AEs (eg, any new event or worsening in severity or frequency of a pre-existing condition or laboratory finding) with an onset date after the subject signs consent for study participation must be promptly documented on the AE CRF. Details of the event must include severity, relationship to study drug, duration, action taken, and outcome. SAEs will be recorded on

the AE CRF *and* on the SAE reporting form (see [Section 9.5](#), Serious Adverse Event Reporting and Documentation Requirements).

AEs will be collected from the time the subject signs informed consent through 30 days following the last dose of study drugs, or initiation of a new anti-cancer therapy. In addition, the Investigator should report any AE (per instructions described above) that may occur after this time period that is believed to have a reasonable possibility of being associated with study drug.

All AEs that are considered related to study drug must be followed to resolution or stabilization if improvement is not expected. AEs which completely resolve and then recur should be recorded as a new AE. For subjects who complete the end-of-treatment visit less than 30 days following their last dose of protocol-defined therapy, a follow up of ongoing AEs should be attempted by telephone, and documented in the subject's source file.

AEs continuing at 30 days after the last dose should have a comment in the source by the Investigator that the event has stabilized or is not expected to improve.

The Principal Investigator is responsible for evaluating all AEs, obtaining supporting documents, and determining that documentation of the event is adequate. AEs will be assigned a severity grade using the NCI-CTCAE grading scale Version 3.0. Any laboratory finding requiring a therapeutic intervention should also be considered as an AE and reported accordingly.

The Principal Investigator may delegate these duties to Sub-Investigators and must assure that these Sub-Investigators are qualified to perform these duties under the supervision of the Principal Investigator and that they are listed on the Form FDA 1572 or Canadian Qualified Investigator Undertaking Form (QIU).

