6.4.2 ALLOWED CONCOMITANT MEDICATIONS

Commercially available bisphosphonates are permitted. Subjects may receive antiemetics and antidiarrheals as necessary, but these should not be administered unless indicated.

Colony-stimulating factors may be used if neutropenia occurs but should not be given prophylactically.

Subjects may receive platelet transfusions in accordance with institutional guidelines.

Red blood cell (RBC) transfusions or supportive care with erythropoietin or darbepoetin alfa, in accordance with institutional guidelines, is also permitted.

Subjects who received 4 mg dexamethasone prior to carfilzomib dosing on an ongoing basis during their previous carfilzomib treatment protocol may continue to receive 4 mg dexamethasone prior to carfilzomib dosing on the current protocol at the investigator's discretion.

The addition of certain approved agents with known antitumor activity is permitted if there is concern for disease progression and per Investigator discretion in consultation with the Onyx Medical Monitor.

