10.2.1 PRIMARY ENDPOINTS (SAFETY)

- Reported peripheral neuropathy AEs (all Grades)
- Reported Grades 3 and 4 AEs
- SAEs
- Grades 1 through 4 AEs leading to a missed carfilzomib dose or a carfilzomib dose reduction or discontinuation

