APPENDIX A: SCHEDULE OF EVENTS

Visit	Screening (Day -30 to -1)	Cycle 1	Every Cycle	Cycle 3 and Every 3 Cycles	End of Study (Within 30 days of last dose of study drug)
Written Informed Consent	X				
Inclusion/Exclusion Criteria	X				
Obtain Previous PX-171 Protocol Unique Identifier	X				
Pregnancy Test ¹	X				
Routine Physical Examination	X				X
Height, Weight, and BSA ²	X		Day 1		
ECOG Performance and Neuropathy Grade	X				
Bone Marrow Sample for Cytogenetics and FISH ³	X				X
CBC + Platelet Count and Serum Chemistry ⁶		Day 1	Day 1	Day 1	
Carfilzomib Dosing (the same dose level and frequency as administered at the last visit of the prior Onyx study)		Days 1, 2, 8, 9, 15, 16, or same dose level and frequency as prior study	Days, 1, 2, 8, 9, 15, 16, or same dose level and frequency as prior study	Days, 1, 2, 8, 9, 15, 16, or same dose level and frequency as prior study	
Disease Assessments (Extent of disease measurements and response), per method employed in previous protocol ⁴	X			Day 1	X
Peripheral Neuropathy AEs (all Grades)	X	X	X	X	X
Grade 3 and 4 AEs, SAEs or AEs Resulting in Missed Dose or Dose Reduction (all Grades) ⁵	X	X	X	X	X
Record any concomitant chemotherapy reagent	X	X	X	X	X

1 Females of childbearing potential must have a negative serum or urine pregnancy test, with a sensitivity of at least 50 mIU/mL, within 3 days prior to dosing.

2 Height done at screening visit only; BSA calculated Day 1 of every cycle. However, dose adjustments not needed for weight gains/losses of $\leq 20\%$.

3 Screening bone marrow aspirate or biopsy for cytogenetics and FISH is optional and is for MM subjects whose disease status at study entry is PR or less. A Bone marrow sample is also optional for all MM subjects at the end of study if there is evidence of disease progression.

4 If disease assessments are done previously within 30 days of first dose of extended study drug, they will not be required again at screening. If disease assessments per standard institutional practices occur more frequently than every 3 months (eg, every month or every 2 months), the most recent assessment may be reported.

5 Record all AEs leading to missed dose, dose reduction or discontinuation. Record all Grade 3 and 4 AEs from time of consent through 30 days post last administered dose of study drug or initiation of a new anti-cancer therapy.

6 CBC + Platelet Count and Serum Chemistry data will not be routinely recorded on CRFs.

**Appendix B: ECOG Performance Scale

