Section 7.7 End of Study Assessments Section 8 Study Discontinuation	Bone marrow aspirate and/or biopsy for cytogenetic and FISH analysis (only required for MM subjects whose reason for study discontinuation is PD).	OPTIONAL: Bone marrow aspirate and/or biopsy for cytogenetic and FISH analysis (only required for MM subjects whose reason for study discontinuation is PD).	Revision. To allow bone marrow biopsies for cytogenetic and fluorescence in situ hybridization (FISH) to be optional, rather than required, for MM subjects whose reason for study discontinuation is PD. To accommodate subjects where bone marrow biopsies are unfeasible or unsafe to obtain.
Section 7.9.1 Cytogenetic and FISH Studies Appendix A Footnote	A bone marrow biopsy and/or aspirate for determining percent plasma cell involvement, including metaphase cytogenetic and FISH studies, are mandatory for all MM entering with a PR, MR, or SD. Samples for cytogenetic and FISH analysis will also be required for all MM subjects who discontinue study due to PD.	A bone marrow biopsy and/or aspirate for determining percent plasma cell involvement, including metaphase cytogenetic and FISH studies are optional for all MM subjects entering with a PR, MR, or SD. Samples for cytogenetic and FISH analysis will also be optional for all MM subjects who discontinue study due to PD.	Revision. To allow bone marrow biopsies for cytogenetic and fluorescence in situ hybridization (FISH) to be optional, rather than required, for MM subjects entering with a PR, MR, or SD and for MM subjects who discontinue study due to PD. To accommodate subjects where bone marrow biopsies are unfeasible or unsafe to obtain.

Section No.	Amendment 2	Amendment 3	Rationale
Section 9.3 Adverse Events Reporting Procedures	AEs will be collected from the time the subject signs informed consent through 30 days following the last dose of study drugs.	AEs will be collected from the time the subject signs informed consent through 30 days following the last dose of study drugs, or initiation of a new anti-cancer therapy.	Addition. To include information/instruction regarding collection of AEs. AEs should not continue to be recorded /collected if a subject initiates a new anti-cancer therapy.

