7.4 Regimen Change

The number and percent of subjects who had regimen change during the study and reasons for regimen changes will be summarized as collected on regimen change case report form. In addition, type of regimen changes: carfilzomib dose level increased/decreased, dose frequency increased/decreased, or other anti-myeloma drugs added will be summarized .

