7.7.2 Progression Free Survival (PFS)

PFS is defined as number of days between start of treatment and first evidence of documented disease progression or death (due to any cause), whichever occurs first. Disease progression will be determined by the local investigator for regimens with the same baseline using the International Uniform Response Criteria ([Durie et al. 2006, with corrections](#)) (IMWG-URC) for multiple myeloma subjects and RECIST criteria ([Therasse et al. 2000](#)) for solid tumor subjects. PFS will be re-calculated whenever the baseline is reset due to addition of new anti-cancer therapy or increase of carfilzomib dose/frequency:

- 1) For regimens that continue from initial study without baseline being reset, if subjects didn't progress before PX-171-010, then PFS for the period from initial study to PX-171-010 study will be calculated as Disease Progression /Death Date – Date of first dose in initial study + 1 day, and PFS for the period of PX-171-010 study only will be calculated as Disease Progression /Death Date – Date of first dose in PX-171-010 + 1 day.
- 2) For regimens that start in PX-171-010 study with baseline being reset from initial study or previous regimens, PFS will be calculated as Disease Progression /Death Date –

Date of first dose in the first regimen among the regimens with common baseline + 1 day.

PFS will be right-censored for subjects who met one of the following conditions: 1) no baseline disease assessments or any post-baseline assessments, 2) alive and does not have documentation of disease progression before a data analysis cutoff date. The PFS censoring rules are described in Table 1.

Table 1. Censoring Rules for PFS Analysis

Situation	Date of Progression or Censoring	Outcome
No baseline disease assessments or any post-baseline assessments	Date of first dose	Censored
Alive and without documentation of disease progression	Date of last disease assessment	Censored
Death or disease progression between planned disease assessments	Date of death or first disease assessment showing disease progression, whichever occurs first	Progressed
Death or PD immediately after more than 1 consecutively missed disease assessment visit*	Date of last disease assessment before the first missed visit	Censored
Death before first disease assessment	Date of death	Progressed

* If death or PD is more than 168 days after previous disease assessment, or the first dosing date if there is no previous disease assessment.

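### The stop on AE collection at a new anti-cancer therapy is not limited to therapy begun after carfilzomib ends, so it can be read to cover subjects who add an agent while still on carfilzomib

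*Protocol*

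**What the plan says.** Protocol Section 9.3 collects AEs from consent "through 30 days following the last dose of study drugs, or initiation of a new anti-cancer therapy". Appendix A footnote 5 sets the same limit for Grade 3 and 4 AEs: "through 30 days post last administered dose of study drug or initiation of a new anti-cancer therapy". The rationale given in Appendix F for the current wording is just as unconditional: "AEs should not continue to be recorded /collected if a subject initiates a new anti-cancer therapy".

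Protocol Section 6.4.2, on allowed concomitant medications, states: "The addition of certain approved agents with known antitumor activity is permitted if there is concern for disease progression". The SAP treats such an addition as an expected event. Section 7.4 lists it among the types of regimen change ("or other anti-myeloma drugs added will be summarized"), and Section 5.5 resets the disease baseline when it happens. Section 7.7.2 says: "PFS will be re-calculated whenever the baseline is reset due to addition of new anti-cancer therapy or increase of carfilzomib dose/frequency". Section 7.7.3 uses the same term for TTP.

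Safety is the primary endpoint. Protocol Section 10.2.1 has four components: peripheral neuropathy AEs of any grade, "Reported Grades 3 and 4 AEs", SAEs, and AEs that lead to a missed dose, a reduction or discontinuation. None is limited to events related to study drug.

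**The concern.** The event that ends AE collection in Section 9.3 carries the same name as an event that the plan permits while carfilzomib is still being given. A site that applies Section 9.3 as written could stop recording non-serious AEs on the day an agent is added, with months of carfilzomib still to come. Another site could follow the visit lists and go on recording. Nothing in the analysis plan would separate the two.

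Any loss would run in one direction. A subject who adds an agent stays in the denominator, which counts everyone with at least one dose (Protocol Section 10.4.1, SAP Section 7.6.1). The later carfilzomib doses still count as exposure (SAP Section 7.5). Missing events can therefore only lower the reported incidence, the per-cycle rates and any exposure-based rates that Section 10.4.1 allows. The loss would also fall late in treatment, in a study whose objective is long-term safety.

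**Working it through.** There is no figure in the plan to reproduce: no hypothesis, no power calculation, and about 100 subjects as an anticipated roll-over count. The check is a comparison of texts, followed by an illustration on assumed inputs.

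**Step 1. Scope of the stop.** Section 9.3 and footnote 5 give two end points joined by *or*. Neither says which prevails, and neither ties the second to permanent discontinuation of carfilzomib.

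**Step 2. What could trigger it.** Section 6.4.2 lists the added agents as concomitant medication, so carfilzomib continues alongside them. The SAP, prepared against Amendment 3, uses the trigger's term for this addition.

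**Step 3. What conflicts with the literal reading.**
- Sections 7.2 to 7.6 require neuropathy AEs, Grade 3 and 4 AEs, SAEs and dose-modifying AEs to be recorded at every dosing visit. Concomitant chemotherapy is on the same lists, with no instruction to stop when it starts.
- SAP Section 7.6.1 counts an AE as treatment-emergent up to 30 days after the last infusion, with no cut at new therapy.

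**Step 4. What would be lost if Section 9.3 were applied literally and the visit lists were not followed.**

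| Component | Section 9.3 sentence | Footnote 5 time limit | Kept by other text | Left exposed |
|---|---|---|---|---|
| SAEs, including deaths | stops | Grade 3 and 4 only | Sections 9.3.1, 9.4, 9.5 | none |
| Non-serious Grade 3/4 | stops | stops | later AEs with a possible link to study drug (Section 9.3) | those not judged related |
| Non-serious neuropathy | stops | none on this row | same | those not judged related |
| Non-serious dose-modifying AEs | stops | none in the footnote's first sentence | same | those not judged related |

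An example in the last row is a non-serious infection that causes a missed dose and is not thought related to carfilzomib.

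**Step 5. Illustration of size.** Let p be the true on-treatment incidence of an AE, f the share of subjects who add an agent, and t the share of exposure elapsed at that time. With a constant hazard and every later event lost:

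observed incidence = (1 − f) × p + f × [1 − (1 − p)^t]

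The documents give none of these inputs; all values here are assumptions.
- p = 20%, f = 30%, t = 50%: 0.7 × 0.20 + 0.3 × (1 − 0.8^0.5) = 0.140 + 0.032 = 17.2%.
- p = 60%, f = 30%, t = 50%: 0.7 × 0.60 + 0.3 × (1 − 0.4^0.5) = 0.420 + 0.110 = 53.0%.
- Over f = 10% to 50% and t = 25% to 75%, the loss is 0.5 to 7.3 percentage points at p = 20% and 1.0 to 19.8 points at p = 60%.

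Within this constant-hazard model, each result is the most that could be lost. It assumes that every site stops recording and that no event is kept as serious or as possibly related.

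**The case against.** The strongest reply is that the clause only shortens follow-up after the last dose. It sits in the same phrase as the 30-day limit. The introduction to Appendix F describes the change as one to AE reporting after the last dose. Section 7.7 places the end-of-study visit before any new therapy, where the term plainly means treatment after the study. The protocol itself never gives an on-study addition this name: it files it under concomitant medication and has sites record it as concomitant chemotherapy. The matching term comes from the SAP's PFS and TTP text, which gives sites no recording rule. Sections 7.2 to 7.6 separately require AE recording at each dosing visit. The study is also descriptive, with no hypothesis (Section 10.1), so no test or decision rule depends on the outcome.

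Most of this stands. It makes the post-treatment reading reasonable, and perhaps the intended one. It does not put that limit into Section 9.3 or footnote 5, and the rationale quoted from Appendix F has no such limit either. The sentence that keeps possibly related later events is only a partial safeguard. It would replace all-cause capture with capture that depends on the investigator's attribution, just when a second agent makes attribution harder.

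A reader might infer that the rule switches off the primary endpoint in these subjects. The documents do not support that. SAEs and deaths have their own windows, possibly related AEs remain reportable, and the visit lists still call for recording. Footnote 5 sets a time limit only for Grade 3 and 4 AEs, so only the Section 9.3 sentence could reach lower-grade neuropathy or dose-modifying events.

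**Conclusion.** The point holds as an ambiguity and an internal contradiction in how the primary endpoint is collected. On one available reading, recording of non-serious AEs not judged related ends while carfilzomib continues. On the other, it does not. Loss of data is possible, not certain, and would bias incidence downward if it happened.

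Its size cannot be derived from the documents, which give no frequency or timing of added agents and no AE rates. The percentages in the illustration show scale under stated assumptions and are not estimates for this study. A reader might also infer that the affected subjects have more AEs than the rest. Section 6.4.2 says only that agents are added over concern about progression. That makes any loss non-random with respect to disease course, but it says nothing about AE rates.

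**What to change.** In Section 9.3, and correspondingly for Grade 3 and 4 AEs in Appendix A footnote 5, use wording such as:

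*AEs are collected from consent until 30 days after the last dose of carfilzomib. Collection of non-serious AEs ends earlier if an anti-cancer therapy is started after carfilzomib has been permanently discontinued. Agents added under Section 6.4.2 while carfilzomib continues do not end AE collection. SAEs are collected until 30 days after the last dose in all cases, as in Section 9.5.*

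The exemption for SAEs is needed. Section 9.3 lists SAEs among the events it covers, so simply adding a whichever-is-earlier clause would create a new conflict with Section 9.5. The existing sentence on later, possibly related AEs should stay.

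Two short SAP additions would help. Section 7.6.1 should note that its 30-day window can outlast non-serious AE collection when new therapy starts after carfilzomib ends. AEs could also be tabulated before and after an agent is added.

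The cost is a few sentences in Section 9.3, one footnote and some extra AE entry at sites that would have stopped early. No treatment rule changes.

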7.7 END OF STUDY ASSESSMENTS (WITHIN 30 DAYS OF STUDY DISCONTINUATION)

The following assessment must be completed within 30 days of administration of last dose of study drug and prior to initiation of any new therapy:

1. Perform complete physical examination
2. Perform Disease Assessments, ie, extent of disease measurements (per method employed in previous protocol); and response category (see [Appendix D–E](#)).
3. OPTIONAL: Bone marrow aspirate and/or biopsy for cytogenetic and FISH analysis (only required for *MM* subjects whose reason for study discontinuation is PD).
4. Record peripheral neuropathy AEs (all grades)
5. Record Grade 3 and 4 AEs, and all SAEs
6. Record any concomitant chemotherapy agents

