9.5 SERIOUS ADVERSE EVENT REPORTING AND DOCUMENTATION REQUIREMENTS

Onyx Therapeutics, Inc. must be notified by telephone or fax of the occurrence of any SAE within 24 hours of the Investigator, designee, or site personnel knowledge of the event.

To report an SAE, call or fax an SAE form to:

Attn: i3 Research
[contact]
SAE [contact]
E-mail: [contact]

Telephone reports must be followed by a written report within 24 hours. Follow-up reports must be submitted in a timely fashion as additional information becomes available.

The Investigator is responsible for notifying the Institutional Review Board (IRB) or Independent Ethics Committee (IEC) in accordance with local regulations, of all SAEs. The sponsor may request additional source documentation pertaining to the SAE sent to Onyx. If a subject is permanently withdrawn from the study because of a SAE, this information must be included in the initial or follow-up SAE report form as well as the Study Discontinuation CRF.

All SAEs occurring from the time that the subject signs consent for study participation or up to 30 days after the last administered dose of study drug will be reported. All SAEs regardless of relationship to study drug must be followed to resolution or to stabilization if improvement or resolution is not expected.

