7.6.1 Adverse Events (AEs)

Treatment emergent adverse events (TEAEs) are defined as AEs that start on or after the first administration of study drug and within 30 days of the last infusion of study treatment. An AE that is present before the first administration of study treatment and subsequently worsens in severity during treatment is also considered to be treatment emergent.

Missing and partially missing AE start dates will be imputed according to the specifications described in Section 7.7.2 of the SAP. Each reported AE term will be mapped to a preferred term (PT) and a system organ class (SOC) using the Medical Dictionary for Regulatory Activities (MedDRA, version 8.1).

Adverse events will be summarized based on the number and percentage of subjects experiencing events by MedDRA SOC and PT. The denominator for the percentage will be based on the number of subjects at risk (i.e., those that received at least one dose of

carfilzomib). The causal relationship of the AE to the study drug will be judged by the investigator as none, unlikely, possible, or probable.

A subject reporting the same AE more than once will be counted only once when calculating 1) within a given system organ class, and 2) within a given system organ class and preferred term combination. For such cases, the maximum National Cancer Institute (NCI; US)-Common Terminology Criteria for Adverse Events (CTCAE, Version 3) toxicity grade and strongest causal relationship to study treatment for the event will be used in the incidence calculations. AEs will also be summarized by severity and by relationship to carfilzomib.

Tabular summaries of the following AEs will be provided by SOC and/ or PT:

- Overall summary of treatment emergent adverse events
- Treatment emergent adverse events
- Treatment emergent adverse events by maximum severity
- Treatment emergent adverse events grade 3 or higher
- Treatment emergent adverse events by relationship to study drug
- Serious treatment emergent adverse events
- Treatment emergent adverse events that led to dose reduction
- Treatment emergent adverse events that led to permanent discontinuation of study drug

All AEs, including treatment emergent events, will be included in listings by subject.

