7.7.1 Overall Survival (OS)

Duration of OS is defined as the days from the start of treatment (initial study) to death due to any cause. For subjects who are alive at the time of the data cut-off, duration of OS will be censored as of the date the subject was last known to be alive.

Since the subjects will be followed up till 30 days after administration of last dose of study drug only per protocol, OS will be calculated and presented in a listing, no Kaplan-Meier estimates will be provided. Number and percentage of subjects who died within 30 days after administration of last dose of study drug will be calculated and death reason will be summarized.

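### After an end-of-study visit held before Day 30, no scheduled contact asks about new events or vital status, so the SAP's 30-day TEAE and death counts may run low

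*Protocol*

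**What the plan says.** Day 30 here means 30 days after the last dose.

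- **Duty to collect.** Protocol 9.3 collects AEs from consent "through 30 days following the last dose of study drugs, or initiation of a new anti-cancer therapy". Protocol 9.5 says that SAEs from consent "up to 30 days after the last administered dose of study drug will be reported", with no new-therapy cut-off. Sections 9.3.1 and 9.4 make every death within 30 days of dosing a reportable SAE, and 9.4 says this holds even if the subject has already left the study. Section 3.4 treats the subject as on study until Day 30 for safety follow-up.
- **Last scheduled visit.** Protocol 7.7 says the end-of-study assessments "must be completed within 30 days of administration of last dose of study drug and prior to initiation of any new therapy". No earliest day is set.
- **Contact after an early visit.** For subjects whose visit comes before Day 30, Protocol 9.3 says "a follow up of ongoing AEs should be attempted by telephone", with a note in the source file.
- **Use in the analysis.** SAP 7.6.1 counts as treatment-emergent the AEs that start on treatment or "within 30 days of the last infusion of study treatment". Protocol 10.4.1 uses the same 30-day limit. SAP 7.7.1 gives no Kaplan-Meier estimate for OS; it lists OS and adds: "Number and percentage of subjects who died within 30 days after administration of last dose of study drug will be calculated".
- **End-of-study checklist.** The AE items in Protocol 7.7 are neuropathy, Grade 3 and 4 AEs, and SAEs. Appendix A also marks its row for dose-affecting AEs at End of Study, and footnote 5 says "Record all AEs leading to missed dose, dose reduction or discontinuation".

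**The concern.** Safety is the primary endpoint, and its main tables depend on what happened up to Day 30. A reporting duty works only once the site knows of the event. After an early visit, the plan gives the site one prescribed route to that knowledge: a call that need only be attempted and is framed around events already open. A subject with no open AE has no prescribed contact at all. Survival status is not part of the call.

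An event missed in this way leaves the numerator but not the denominator, because the subject still counts as treated. The error therefore runs in one direction, towards too few TEAEs and too few deaths. Apart from the OS listing and the summary of death reasons, the 30-day death percentage is the only survival summary the SAP plans.

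Two smaller mismatches sit beside this. The SAP's treatment-emergent window runs a flat 30 days, whereas AE collection under 9.3 can stop earlier, at new anti-cancer therapy. And the 7.7 checklist leaves out one component of the primary endpoint.

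**Working it through.** The plan gives no figure to reproduce; this is a check of ascertainment. The inputs are Protocol 3.4, 7.1 to 7.7, 8, 9.3 to 9.5, 10.4.1 and Appendix A, and SAP 7.1, 7.6.1, 7.7 and 7.7.1.

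**Step 1. Duty against scheduled contact, after a visit before Day 30**

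| Item | Duty runs to | Scheduled contact after the visit | Counted to |
|---|---|---|---|
| AE open at the visit | Day 30 or new therapy (9.3) | Attempted call (9.3) | Onset is already before the visit |
| New reportable AE, not serious | Day 30 or new therapy (9.3) | None | Day 30 (SAP 7.6.1) |
| New SAE | Day 30 (9.5) | None | Day 30 (SAP 7.6.1) |
| Death | Day 30 (9.3.1, 9.4) | None | Day 30 (SAP 7.7.1) |

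The one scheduled contact serves the row that adds no new onset to the TEAE count. The other three rows rest on duty alone. Protocol 8 says that discontinued subjects are monitored for AEs, but it points to Appendix C, which only cites the CTCAE and sets no contact.

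**Step 2. Length of the gap**

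For a visit on Day v, the days without a scheduled contact for new events are 30 − v, and the share of the window is (30 − v)/30. The visit days below are assumptions.

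- v = 7: 23 days, 23/30 = 77%
- v = 14: 16 days, 16/30 = 53%
- v = 21: 9 days, 9/30 = 30%
- v = 25: 5 days, 5/30 = 17%
- v = 30: 0 days

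If new anti-cancer therapy starts on Day t, routine AE collection ends there. The gap for non-serious AEs is then min(30, t) − v. With v = 7 and t = 14 (assumed), that is 14 − 7 = 7 days, while the gap for SAEs and deaths stays at 23. These are shares of time, not shares of events lost.

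**Step 3. Weight of one missed death**

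One missed death lowers the 30-day percentage by 1/n. For n of about 100, the planned enrolment, that is 1 percentage point. SAP 7.1 and 7.7 report efficacy separately for the myeloma and solid-tumor cohorts, so each reported n will be smaller. Cohort sizes are not given; with an assumed n of 20 the shift is 1/20 = 5 points.

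**Step 4. The checklist**

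The item for AEs of any grade that affect dosing or end treatment appears in each list from 7.1 to 7.6 and is absent from 7.7. Protocol 9.3 makes these AEs reportable. Appendix A marks the row at End of Study; its label names missed and reduced doses, and footnote 5 adds discontinuation. A Grade 1 or 2, non-serious, non-neuropathy AE that ended treatment therefore matches no item in 7.7, although two other places require it.

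**The case against.** The strongest reply is that the window is covered. Collection or reporting through Day 30 is stated for AEs, SAEs and deaths, and for deaths explicitly after the subject has left the study. A reader might infer from the narrow call that events after the visit are never sought. The documents do not support that: the duties in 9.3, 9.3.1, 9.4 and 9.5 stand, deaths are the best protected item, and nothing stops a site from asking about new events on the call. What remains is that the plan relies on the site learning of the event without scheduling the question.

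A second reply concerns subjects who leave for another treatment. Their visit must come before that treatment and so may be early, but routine AE collection stops when it starts. Later non-serious events in these subjects are excluded by design and are not missed. This is correct. It narrows the concern for such subjects to SAEs, deaths and the days between the visit and the new therapy. It also means that a call asking every subject about all new AEs to Day 30 would contradict 9.3.

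Third, a reader might infer from 7.7 that AEs leading to discontinuation need not be recorded. Section 9.3 and Appendix A footnote 5 require them, the dosing-visit lists capture them, and Section 8 puts the reason for withdrawal on the CRF. The omission is an internal inconsistency, and loss of a primary component is not shown.

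**Conclusion.** The point holds as a gap between a stated duty and the procedure behind it. After an end-of-study visit before Day 30, new AEs, new SAEs and vital status have no scheduled ascertainment, yet the SAP counts them to Day 30. Any resulting bias in the TEAE and 30-day death counts is downward.

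Its size cannot be estimated from the documents, which give no distribution of visit days, no cohort sizes and no event rate after the visit. The exposed part of the window runs from nothing, for a Day 30 visit, to nearly all of it for a visit just after the last dose. It is shorter for non-serious AEs when new therapy starts early. The 1-point and 5-point effects of a single missed death rest on n of about 100 and an assumed n of 20.

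The difference between the flat 30-day TEAE window and the new-therapy cut-off in 9.3, and the missing line in 7.7, are inconsistencies to reconcile. The change is worth making because it is cheap and bears on the primary endpoint.

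**What to change.** - **Protocol 9.3.** Replace the call about ongoing AEs with a contact at Day 30 (plus a few days), recorded on the CRF, for every subject whose end-of-study visit is before Day 30. In all of them, ask about vital status and SAEs up to Day 30. Ask about new as well as ongoing reportable AEs with onset up to Day 30 or the start of new anti-cancer therapy, whichever comes first, as 9.3 already limits.
- **Same contact.** Record the first subsequent regimen and its start date. Section 3.1 promises data on that regimen, but no visit list in Section 7 or Appendix A includes it, and the last visit must precede it. The start date is also needed to apply the AE cut-off. The CRFs were not available, so they may already hold a field for this.
- **SAP 7.6.1 and Protocol 10.4.1.** Align the treatment-emergent window with the new-therapy cut-off in 9.3, and state that SAEs and deaths run to Day 30.
- **Protocol 7.7.** Add the item on AEs of any grade leading to a missed dose, a reduction or discontinuation, so that it matches 9.3 and Appendix A footnote 5.

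The cost is protocol and SAP wording, one CRF page and one short call per early-visit subject. The reported event rate may rise slightly.
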